### **3.4 Procedures for handling incorrectly enrolled or randomized subjects**

Subjects incorrectly enrolled or randomized subjects will be withdrawn from the study. These subjects:

- will be apologized,
- will be administered double antiplatelet therapy with ASA and a P2Y12 antagonist, as well as other medications, if required,
- will be asked to return the study medication, if identified after the study medication has already been dispensed,
- will be monitored in the same way as subjects continuing the study until the last visit at 6 months.

The PI will maintain a list of incorrectly enrolled or randomized subjects in the Investigator's Study File.

### **3.5 Methods for assigning treatment groups**

Upon successful randomization, the subject will be assigned a randomization number and treatment. The subject’s identification data and ID number, and randomization number will be

listed on the Patient Identification List and Patient Enrolment List, respectively, and stored in the Investigator's Study File.

### **3.6 Methods for ensuring blinding**

Not applicable to study subjects. The PI will be blinded to the randomization arm and treatment of study subjects. The operator analyzing the samples will be blinded to all subject-related baseline and clinical data.

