### **3.7 Methods for unblinding**

Not applicable for patients. The PI will be unblinded by combining the Patient Identification List including subjects identification data and Patient Enrolment List including data on subjects randomization

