#### 6.1.4 Causality assessment

The causality of AE in relation to study treatment will be assessed by the PI, who in completing the relevant AE Report Form will answer ‘yes’ or ‘no’ to the question “Do you consider that there is a reasonable possibility that the event may have been caused by the study medication?” Causality will be assessed using the following definitions:

- Very likely
  - The AE follows a reasonable temporal sequence from study treatment administration;
  - Abates upon discontinuation of study treatment;
  - Reappears on repeated exposure (re-challenge).
- Probable
  - The AE follows a reasonable temporal sequence from study treatment administration;
  - Abates upon discontinuation of study treatment;
  - Cannot reasonably be explained by known characteristics of the subject's clinical state.
- Possible
  - The AE follows a reasonable temporal sequence from study treatment administration, but could have been produced by the subject's clinical state or other mode of therapy administered to the subject.
- Doubtful
  - The temporal association between study treatment and AE is such that the study treatment is not likely to have any reasonable association with the observed event.
- Very unlikely
  - The AE is definitely produced by the subject's clinical state or other mode of therapy administered to the subject.

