## 7.4 Storage

The investigational product will be stored in accordance with the manufacturers' instructions. Required conditions for storage will be printed on the medication label. The temperature within the load will be measured at least twice daily and recorded in the Investigator's Study File. Investigational product will be kept under adequate security by the PI and only accessible to authorised study personnel.

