## 7.6 Accountability

The PI will maintain current record of the receipt, inventory and dispensing, including shipping invoices, of all study supplies. The Investigational Product Accountability File will include:

- Date received
- Reference number and amount received and placed in storage
- Name of study medication and dosage
- Label ID number or batch number
- Name of person responsible for each investigational product inventory entry
- Amount dispensed to and returned by each subject, including unique subject identifiers
- Non-study disposition (e.g. lost, wasted, broken)
- Amount returned to Sponsor

Accountability files will be available for inspection by the monitor at any time. Upon completion/ termination of the study, unused investigational product will be returned to the Sponsor reconciliation.

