### **10.2 Subject data protection**

The PI will assure that the subjects' anonymity will be maintained and that the confidentiality of records and documents that could identify subjects will be protected, respecting the privacy and confidentiality rules in accordance with applicable regulatory requirements. Before unblinding of the PI, subjects will be identified only by their assigned identification number and initials. A co-investigator will keep a Patient Identification List with complete identification information (name, address, contact number).

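### The PI is declared blinded to arm and treatment, but the PI's drug-custody and record-keeping duties mean that this blinding cannot be maintained as written

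*Combined protocol and SAP*

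**What the plan says.** Section 3.6 says that blinding does not apply to subjects, but "The PI will be blinded to the randomization arm and treatment of study subjects". It adds that the operator who analyses the samples is blinded to subject data. Section 1.2 cites investigator-blinded allocation in support of reliability. The synopsis calls the study open-label.

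Other sections give the PI these duties:

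- **Storage (7.4):** "Investigational product will be kept under adequate security by the PI and only accessible to authorised study personnel".
- **Accountability (7.6):** "The PI will maintain current record of the receipt, inventory and dispensing". The file lists the name and dosage of the medication, and "Amount dispensed to and returned by each subject, including unique subject identifiers".
- **Source data (9.2.1):** pharmacy dispensing records count as source data, and the PI maintains the source documents for each patient.

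On the key that links subject to arm, Section 3.7 says: "The PI will be unblinded by combining the Patient Identification List including subjects identification data and Patient Enrolment List", the latter holding the randomisation data. Section 3.5 has the identity data and the randomisation number "listed on the Patient Identification List and Patient Enrolment List, respectively, and stored in the" Investigator's Study File, and Section 9.3 includes both lists among that file's contents. Section 10.2 says instead: "A co-investigator will keep a Patient Identification List with complete identification information".

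The PI also makes judgements that knowledge of the arm could colour. Section 6.1.4 says: "The causality of AE in relation to study treatment will be assessed by the PI". Section 6.1.3 has the PI assign the CTCAE grade.

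**The concern.** Blinding an investigator works only if the tasks that reveal treatment belong to someone else. Here they are assigned to the person who is said to be blinded. If the protocol is followed literally, a report repeating Sections 1.2 and 3.6 would describe a protection that the procedures do not deliver.

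At stake are the steps that laboratory blinding does not reach. These are the grading and causality of adverse events, the PI's discretion to stop study drug (3.9), and withdrawal for any reason in the investigator's opinion, with replacement (3.10). The PI's preparation of plasma (5.7.3) is also exposed, and Section 9.1 treats sample handling as a possible source of variability.

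**Working it through.** The point turns on consistency between sections, so there is no planned figure to reproduce.

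**Step 1: does the PI's work reveal treatment, leaving the lists aside?**

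| Duty or fact | Section | What it reveals |
|---|---|---|
| PI keeps the product | 7.4 | Physical access to both drugs |
| PI maintains the dispensing record; the file holds drug name and amounts per identified subject | 7.6 | Which subject received which drug |
| PI maintains source documents; dispensing records are source data | 9.2.1 | The same link by a second route |
| Tablets of 90 mg and 75 mg from different manufacturers | 7.1 | The products can be told apart |
| Box label identifies the product; no masking described | 7.3 | The box shows the treatment |

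Sections 7.4 and 7.6 are enough by themselves to contradict Section 3.6.

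**Step 2: do the lists protect the blinding?** Section 3.7 makes combining the two lists the act that unblinds the PI. Sections 3.5 and 9.3 put both in the Investigator's Study File. The PI keeps other documents in that file: the list of incorrectly enrolled subjects (3.4), the screening failures (3.10.1) and the consent originals (10.4). Section 9.3 places the Accountability File there too. Section 10.2 gives the Patient Identification List to a co-investigator and says that subjects carry only a number and initials until the PI is unblinded. These sections disagree. Even if 10.2 prevails, the safeguard is weak, because the PI enrols the subjects (3.3) and informs them for consent (10.4), and so already knows who they are. The list that matters is the Patient Enrolment List, and 10.2 does not move that one.

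**Step 3: which measurements are exposed?** The flow-cytometry reading has its own blinded operator, and coded samples are analysed in one block (3.6, 5.7.2). Plasma preparation comes before that step and is the PI's alone. With 60 subjects and three samplings (5.7), there are 60 × 3 = 180 preparations. The first sample is timed from the clopidogrel loading dose and the second from randomisation, and the text does not say whether the first comes before randomisation. If it always does, arm cannot affect it, and the exposed number is 60 × 2 = 120. The range is therefore 120 to 180, assuming complete sampling of 60 subjects. This counts opportunities. It does not measure bias.

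**The case against.** The best defence is that the plan already separates several roles. An independent operator randomises (3.3), and a different, blinded operator reads the samples. Section 7.4 allows access by authorised personnel, and 7.6 records who is responsible for each inventory entry, so someone other than the PI could handle drug and make entries. Two other investigators and a nurse are available (9.1). Investigator-blinded allocation in 1.2 may mean only allocation concealment. Safety is reported descriptively (2.3, 8.3.2), and subjects also rate intensity themselves (6.1.3).

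Much of this stands, and it rules out several stronger readings that a reader might infer:

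- **That PI blinding does not exist, or that the PI certainly knows every arm.** The documents show only that blinding cannot be assured as written, since practical delegation is possible.
- **That the PI maintains the whole Investigator's Study File.** Section 9.3 names nobody. Other sections place only particular PI documents in it.
- **That the primary comparison is biased by a calculable amount.** Any figure would need an assumed link between discretionary withdrawal and vesicle concentration, and the documents give none. It would also assume that withdrawn subjects' data are lost, whereas 3.9.1 continues assessments after study drug is stopped and 8.1 analyses all randomised patients with meaningful data.
- **That all discretionary removals are the PI's.** Section 3.9 names the PI (or the subject) for stopping drug, but 3.10 refers to the investigator, and there are three.

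The defence does not remove the contradiction. Possible delegation is not planned delegation, and 7.6 and 9.2.1 give the revealing records to the PI by role. The allocation-concealment reading may rescue 1.2, but it does not rescue 3.6, which covers treatment as well as arm.

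**Conclusion.** The concern holds as an internal contradiction: a stated design property cannot be maintained under the procedures that the protocol assigns. This rests on reading 7.4, 7.6 and 9.2.1 as written, with no unstated delegation. The conflict between 3.5/9.3 and 10.2 on list custody is a second, smaller inconsistency.

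The practical reach is limited. The reading of the primary variable stays blinded. PI-assessed adverse events, decisions to discontinue or withdraw, and the handling of post-randomisation plasma should be regarded as made without assured blinding. No mechanism by which plasma preparation would differ by arm is described, and no numerical size of bias can be derived. The plan should be corrected, but the point does not invalidate the primary endpoint.

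**What to change.** **Preferred.** In 3.5, 7.4, 7.5, 7.6, 9.2.1 and 9.3, assign product custody, dispensing, blister counts, the Accountability File, the dispensing source records and the Patient Enrolment List to the independent operator who randomises, or to an existing co-investigator. Hold them apart from any file that the PI uses until database lock, and keep a documented route to unblind earlier for safety. Reconcile 3.5 and 9.3 with 10.2 on who holds the Patient Identification List.

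**Otherwise.** Delete the PI-blinding claim in 1.2, 3.6 and 3.7, and describe the trial as open-label with blinded sample analysis only.

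**Cost.** The first option needs protocol wording and some delegation among staff already named, with no added visits or subjects. The second costs only a less favourable description of the design.

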### **3.7 Methods for unblinding**

Not applicable for patients. The PI will be unblinded by combining the Patient Identification List including subjects identification data and Patient Enrolment List including data on subjects randomization

### **3.8 Restrictions.**

Not stated.

### **3.9 Discontinuation of investigational product**

The investigational product (IP) may be discontinued at any time at the discretion of the PI or the study subject. Criteria for discontinuing the investigational product include:

- Withdrawal of informed consent.
- Development of exclusion criteria, pregnancy or other safety reasons during the study (requirement of unacceptable concomitant medication, adverse event, intolerance of the IP)
- Protocol non-compliance.
- Incorrect enrolment or randomization of the subject.

#### **3.9.1 Procedures for discontinuation of a subject from investigational product**

For subjects discontinued from the IP, the same measurements and assessments will be performed as in patients continuing the study until the last visit at 6 months, including monitoring of the adverse events. The subjects will be asked to return the study medication.

### **3.10 Criteria for withdrawal**

Criteria for withdrawal from the study include:

- Withdrawal of informed consent.

- Development of exclusion criteria, pregnancy or other safety reasons during the study (requirement of unacceptable concomitant medication, adverse event, intolerance of the investigational product).
- Protocol non-compliance.
- Incorrect enrolment or randomization of the subject.
- Lost to the last visit at 6 months.
- Any other reason, in the investigator's opinion, that would impede the subject's participation in the study

The withdrawn subjects will be replaced by subjects subsequently recruited for the study, until the estimated sample size of the study participants will be achieved.

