## 6.1.3 Variables

The following variables will be collected for each AE;

- Description of AE.
- The date and time when the AE started and stopped.
- The intensity of the AE according as assessed by study subjects according to the following scale:
  - Mild = awareness of sign or symptom, but easily tolerated
  - Moderate = discomfort sufficient to cause interference with normal activities
  - Severe = incapacitating, with inability to perform normal activities.
- The intensity of the AE assessed by PI as CTCAE grade 1-5.
- Whether the AE is serious or not. The AE assessed by the study subject as severe AE is not equivalent to serious AE.
- Causality assessment in relation to study treatment.
- Action taken with regard to investigational product.
- Withdrawal of the subject from the study due to AE.
- Outcome.

In addition, the following variables will be collected for SAEs:

- Date when AE met criteria for serious AE.
- Date Investigator became aware of serious AE.
- The reason why AE is serious.
- Date of hospitalization.
- Date of discharge or death.
- Probable cause of death.
- Autopsy performed.

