## **6.5 Management of toxicities <<Dose Reductions>>**

A subject with confirmed or suspected toxicity of the study medications will be admitted to 1st Chair and Department of Cardiology for assessment and monitoring. After considering of

benefit to risk ratio the drug will be temporarily withheld. If the toxicity continues after re-initiation of the treatment, the drug will be permanently withheld.

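### Sections 3.9 and 3.10 share post-randomisation triggers, but 3.10 allows withdrawal with replacement and does not say that assessment to 6 months continues

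*Combined protocol and SAP*

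**What the plan says.** Section 3.9 lists criteria for stopping the investigational product, at the discretion of the PI or the subject. Section 3.10 lists criteria for withdrawal from the study. Both contain the bullet "Development of exclusion criteria, pregnancy or other safety reasons during the study", with the same three examples in brackets: unacceptable concomitant medication, adverse event, and intolerance. Both also list protocol non-compliance, consent withdrawal and incorrect enrolment or randomisation.

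The stated consequences differ:

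- **Section 3.9.1**, for subjects off the product: "the same measurements and assessments will be performed as in patients continuing the study until the last visit at 6 months".
- **Section 3.10**, for subjects withdrawn: "The withdrawn subjects will be replaced by subjects subsequently recruited for the study", until the estimated sample size is reached. It says nothing about assessment after withdrawal.

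Four other places bear on the point:

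- **Section 3.4** withdraws incorrectly enrolled or randomised subjects, yet they "will be monitored in the same way as subjects continuing the study until the last visit at 6 months".
- **Section 6.1.3** records "Action taken with regard to investigational product" and "Withdrawal of the subject from the study due to AE" as separate variables.
- **Section 6.5** deals with toxicity through the drug alone: "If the toxicity continues after re-initiation of the treatment, the drug will be permanently withheld".
- **Section 8.1** announces an ITT approach covering randomised patients who contributed meaningful data. It does not mention replaced subjects.

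**The concern.** Adverse events, intolerance and non-compliance arise after randomisation and may depend on the drug. Under section 3.6 blinding is "Not applicable to study subjects", so subjects know what they are taking, and their reporting and decisions to stop may differ by arm.

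A site that reads 3.10 as ending a subject's participation would not draw the 6-month sample planned in section 5.7. That subject could not enter the 6-month comparison of PEV concentration under 8.3.5, and a newly recruited subject would fill the place. The 6-month comparison would then rest partly on who tolerated treatment. An ITT statement cannot supply a value that was never measured, and section 8.3.9 plans no sensitivity analysis that would probe such losses. The descriptive safety comparison would also lose later follow-up of the subjects who had problems.

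**Working it through.** **1. The triggers side by side**

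| Trigger | In 3.9 | In 3.10 | Is follow-up after withdrawal stated? |
|---|---|---|---|
| Exclusion criteria, pregnancy, safety reasons | yes | yes | no (6.4.1 follows a pregnancy to its outcome) |
| Protocol non-compliance | yes | yes | no |
| Incorrect enrolment or randomisation | yes | yes | yes, in 3.4, to 6 months |
| Consent withdrawal | yes | yes | 3.10.2, every effort to complete observations |

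The gap is in the first two rows.

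**2. What can be lost.** Section 5.7 plans three samples: 24 h after the clopidogrel loading dose, 48 h after randomisation, and 6 months. No text discards the first two for a withdrawn subject. Only the 6-month sample and later safety follow-up are exposed.

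**3. Illustrative size.** The documents give no event rates, no difference by arm and no PEV deviation for such subjects. Assume k more exits in one arm of 30, each d SD from the retained subjects and replaced by subjects like those retained. The shift in the 6-month arm difference is k × d / 30.

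- k = 0 or d = 0: shift 0.
- k = 3, d = 1: 3 × 1 / 30 = 0.10 SD. With SE = √(2/30) = 0.258 SD, this is 0.10 / 0.258 = 0.39 SE.

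Both k and d are assumptions.

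**4. Is replacement needed for power?** Inputs from 8.2: difference 1, SD 1 per group, two-sided 0.05, power 0.90, total 60. Allocation is 1:1 (3.3). The exact t-test calculation gives 22.02, so 23 per arm and 46 in total. The stated inputs alone therefore do not reproduce 60. The explanation is in Appendix E, which is not in the text reviewed, so 60 is not called wrong here.

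| Subjects per arm | Power |
|---|---|
| 30 v 30 | 0.968 |
| 24 v 24 | 0.924 |
| 23 v 23 | 0.912 |
| 30 v 24 | 0.948 |
| 30 v 18 | 0.907 |
| 30 v 17 | 0.897 |

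With all losses in one arm, power first falls below 0.90 at 13 lost (30 v 17).

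**5. Cost of keeping subjects who stopped the drug.** Assume k of 30 ticagrelor subjects lose the whole effect by 6 months, and let p = k/30. The expected difference is 1 − p. The ticagrelor-arm variance is 1 + p(1 − p). The pooled SD is √((2 + p(1 − p))/2).

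| k | Difference | Pooled SD | Power (30 per arm) |
|---|---|---|---|
| 1 | 0.967 | 1.008 | 0.955 |
| 2 | 0.933 | 1.015 | 0.938 |
| 3 | 0.900 | 1.022 | 0.918 |
| 4 | 0.867 | 1.028 | 0.894 |

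**The case against.** The strongest reply is that the two sections do not conflict. Section 3.9.1 is unconditional for anyone off the product, and a subject withdrawn for an adverse event, intolerance or pregnancy would ordinarily be off it. Section 3.10 adds replacement and never says that assessment stops. Section 3.4 combines withdrawal with monitoring to 6 months. Section 3.10 lists loss to the 6-month visit as a criterion of its own, which suggests that the other criteria do not by themselves mean missing that visit. The separate fields in 6.1.3 show that stopping the drug and leaving the study are distinct events, but not that assessment ends at withdrawal.

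Most of this stands. A reader might infer that the protocol forces a choice between assessment and replacement, and the text does not support that. Continued assessment remains an inference for these triggers, however. The protocol spells out follow-up after withdrawal for incorrect enrolment and promises effort after consent withdrawal, but says nothing for safety reasons or non-compliance.

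Two mitigating points also stand. Section 3.6 blinds the PI, who shares the decision to stop the drug, and the sample operator, so differential exit would come mainly through subjects' own reports and choices. Section 6.1.2 promises every effort to follow unresolved adverse events, which limits the safety loss.

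**Conclusion.** The point holds as a conditional weakness in a stated rule. Section 3.10 permits withdrawal and replacement on post-randomisation events that may depend on treatment and does not say that 3.9.1 assessment continues. If sites take withdrawal to end assessment, the 6-month comparison loses a selected group, against the ITT approach in 8.1. If 3.9.1 is applied to these subjects, the loss largely does not arise.

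The size of any bias cannot be computed from the documents. The range of 0 to 0.10 SD is illustration under assumed counts and deviations. It concerns the 6-month sample only, and 8.3.5 does not name which sampling is primary.

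A reader might also infer that replaced subjects are dropped from the ITT set. The documents do not say so: replacement by itself removes no one, and 8.1 excludes only those without meaningful data.

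The change should be made because it is cheap and the ambiguity falls on the subjects whose data matter most. Confidence is medium, since the harm depends on how 3.10 is read.

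**What to change.** In 3.10, state that randomised subjects who stop the drug for safety reasons, development of exclusion criteria, pregnancy or non-compliance are not withdrawn from the study. They are assessed to 6 months under 3.9.1 unless they withdraw consent. In 8.1, state that all randomised subjects with data are analysed in their randomised arm, whether or not a replacement is recruited. Dropping replacement is optional; under the 8.2 assumptions power does not require it.

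The cost is a short amendment to two sections. It adds no assessments beyond those 3.9.1 already requires and leaves pregnancy follow-up under 6.4 intact. The downside is slight dilution of the 6-month difference by subjects off the drug: power stays above the planned 0.90 if up to 3 of 30 ticagrelor subjects lose the full effect, and falls just below it at 4 of 30. These counts are assumptions.

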### **3.10.2 Withdrawal of the informed consent**

Subjects are free to withdraw from the study at any time for any reason. Should a subject withdraw a consent, every effort will be made to complete and report the observations as thoroughly as possible.

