#### **5.7.4 Withdrawal of Informed Consent for donated biological samples**

Subjects are free to withdraw the Informed Consent for donated biological samples at any time for any reason. The donated biological samples from subjects who withdrew a consent will be excluded from analysis.

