## 8. STATISTICAL ANALYSES

### 8.1 Statistical considerations

A single statistical analysis will be performed at the end of the study by an independent professional statistician from the Epidemiology Department of Medical University o Warsaw using IBM SPSS Statistics 20 and GraphPad Prism 5. An intention to treat (ITT) approach

will followed, i.e. statistical analysis will be based on data from all patients who were randomized and from whom meaningful data were collected. Data will be displayed graphically for visual inspection. Categorical variables will be presented as number and percent; continuous variables will be presented as mean and standard deviation (SD) or median with inter-quartile range. Shapiro–Wilk test will be used to test for non-Gaussian distribution of continuous variables.

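### Sections 3.9.1 and 3.10 give the same four events different consequences, and replacing randomised subjects under a loosely defined ITT set permits an analysis of retained subjects only

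*Combined protocol and SAP*

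**What the plan says.** Section 3.9 lists four reasons for stopping the investigational product: consent withdrawal; a group worded "Development of exclusion criteria, pregnancy or other safety reasons during the study (requirement of unacceptable concomitant medication, adverse event, intolerance of the IP"); protocol non-compliance; and incorrect enrolment or randomisation. For subjects so discontinued, section 3.9.1 states that "the same measurements and assessments will be performed as in patients continuing the study until the last visit at 6 months".

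Section 3.10 gives the same four reasons, almost word for word, as criteria for withdrawal from the study. It adds two more: "Lost to the last visit at 6 months", and any other reason in the investigator's opinion. Its rule for all of them is: "The withdrawn subjects will be replaced by subjects subsequently recruited for the study, until the estimated sample size of the study participants" is reached.

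Three other passages touch the same subjects:
- Section 3.4 says that incorrectly enrolled or randomised subjects are withdrawn, yet "will be monitored in the same way as subjects continuing the study until the last visit at 6 months".
- Section 3.10.2 says that after consent withdrawal "every effort will be made to complete and report the observations as thoroughly as possible".
- Section 5.7.4 contains the only explicit exclusion: "The donated biological samples from subjects who withdrew a consent will be excluded from analysis".

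Section 8.1 describes an intention-to-treat approach based on "all patients who were randomized and from whom meaningful data were collected". It does not say what makes data meaningful. Section 8.3.1, headed as the efficacy analysis set, names an endpoint and no population. Section 8.3.9 plans no sensitivity analysis.

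**The concern.** Section 3.10 turns events that happen after randomisation (adverse events, intolerance, non-compliance, a missed final visit) into grounds for removing a randomised subject and recruiting another until the target is met. That pulls against the 6-month follow-up in section 3.9.1 and against the ITT label in section 8.1. Nothing says which status applies when a shared trigger occurs, or whether a replaced subject stays in the analysis.

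Two teams following this text could therefore analyse different people, either everyone randomised who has a sample or only the 60 who stayed, and both could report the result as ITT. Under section 3.6 the PI and the sample operator are blinded, which limits differences driven by them. Subjects are not blinded and may stop the drug at their own discretion (section 3.9), so subject-driven withdrawal can differ by arm. If those who leave also differ in PEV concentration, a retained-only comparison no longer estimates the effect in the randomised groups.

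**Working it through.** **1. Passages side by side**

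| Event | 3.9 and 3.9.1 | 3.10 | Elsewhere |
|---|---|---|---|
| Consent withdrawn | stop drug, assess to 6 months | withdraw, replace | 3.10.2: complete observations where possible; 5.7.4: samples excluded; 10.4: free to withdraw |
| Exclusion criterion, pregnancy, safety | stop drug, assess to 6 months | withdraw, replace | no linking rule |
| Non-compliance | stop drug, assess to 6 months | withdraw, replace | no linking rule |
| Incorrect enrolment or randomisation | stop drug, assess to 6 months | withdraw, replace | 3.4: withdrawn and monitored to 6 months |
| Lost to 6-month visit | not listed | withdraw, replace | no linking rule |

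Only one of the four shared triggers has a passage (section 3.4) that explicitly joins withdrawal to continued monitoring.

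**2. What the analysis set allows**

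Section 5.7 plans three samplings. A subject who leaves after the 48-hour sample has usable data at that point and none at 6 months. Section 8.1 does not say whether that counts as meaningful. Replacing until 60 are retained means randomising 60/(1 − d), where d is the withdrawal fraction (assumed; the documents give none):
- d = 10%: 60/0.90 = 66.7, so 67 randomised and 7 possibly outside the analysis.
- d = 20%: 60/0.80 = 75 randomised and 15 possibly outside.

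**3. Size of the shift if withdrawn subjects are left out**

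In one arm let f be the fraction withdrawn and k the mean PEV of withdrawn minus retained subjects, in SD units. The all-randomised mean equals the retained mean plus f·k, so

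retained mean − all-randomised mean = −f·k, and

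shift in arm difference = −(f_T·k_T − f_C·k_C).

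Both inputs are assumptions: f from 0.05 to 0.20 in each arm, k from −1 to +1.
- Same k in both arms: largest shift 1 × (0.20 − 0.05) = 0.15 SD; zero when the rates are equal.
- Opposite k, 20% in both arms: 0.20 + 0.20 = 0.40 SD. At 10% in both arms it is 0.20 SD, and at 5% it is 0.10 SD.
- Data kept: zero.

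The 0.15 bound depends on at least 5% withdrawing in each arm. As a separate illustration, suppose withdrawal occurs in one arm only, 30 per arm are retained and there is no true effect (10,000 simulations). With a withdrawal–outcome correlation of 0.3, the bias is 0.07 SD at about 10% withdrawal and 0.11 SD at about 20%, with type I error 6.0% and 7.5%. With correlation 0.5, the bias is 0.11 and 0.17 SD, with type I error 7.7% and 11.1%.

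**4. Is replacement needed for power?**

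Inputs from section 8.2: two-sided 0.05, SD 1, difference 1, power 0.90, total 60.
- Normal approximation: n per arm = 2 × (1.960 + 1.282)² = 21.02, so 22.
- Noncentral t: 22.02, so 23 per arm and 46 in total.

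The stated inputs alone do not reproduce 60. Section 8.2 refers to Appendix E for the explanation, and that appendix is not visible, so I do not call this an error.

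t-test power by numbers analysed: 30/30 0.968; 27/27 0.950; 24/24 0.924; 23/23 0.912; 22/22 0.8997. Losses in one arm only: 30/18 0.907; 30/17 0.897. Section 8.3.5 also allows Mann–Whitney; on normal data, simulated power is about 0.91 at 24/24 and just under 0.90 at 23/23.

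**The case against.** The strongest reply is that the passages overlap rather than conflict. Assessment (3.9.1) and status (3.10) can apply to the same subject, and section 3.4 shows exactly that for one trigger. This stands. A reader might infer a flat contradiction between measuring and withdrawing; the documents show an overlap that is resolved for one trigger and left open for the other three.

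A reader might also infer that the plan calls for an analysis of completers. It does not. No passage orders withdrawn or replaced subjects excluded, and a withdrawn subject with a 48-hour sample fits the wording of section 8.1. Sections 3.4, 3.9.1, 3.10.2 and 8.1 all lean towards keeping data, and if data are kept, replacement by itself causes no such bias. What remains is that nothing forbids a retained-only analysis, and replacement up to a target invites one.

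The 0.40 SD figure is a corner case: it needs 20% withdrawal in both arms and effects of opposite sign. It should not be quoted as an expected bias.

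Finally, section 3.9.1 read literally would require measurement after consent withdrawal. That reading is strained, since 3.10.2 deals with that case and 10.4 protects the right to withdraw. What may be done with such data depends on the consent form, which is not visible.

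**Conclusion.** The point holds in limited form. Sections 3.4, 3.9.1, 3.10 and 3.10.2 must be reconciled, and section 8.1 does not fix who is analysed. The plan permits, but does not require, a retained-only analysis reported as ITT.

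Whether bias would follow depends on two conditions that the documents do not settle: that withdrawn subjects are left out, and that withdrawal relates to both arm and outcome. Its size and direction cannot be computed from the documents; every figure in step 3 of the working rests on assumed withdrawal rates and differences. It is worth correcting before the samples are analysed, because the remedy is cheap and the choice of set should not be open once results are known.

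**What to change.** Without changing any drug-stopping rule:

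- **Sections 3.4, 3.9.1, 3.10, 3.10.2.** Reconcile them so that stopping study drug is separate from leaving the study, and subjects off drug who still consent continue to be sampled. State that data after general consent withdrawal are handled as the consent form allows.
- **Section 3.10.** State that a replaced subject is never removed from the analysis, or drop replacement of randomised subjects; either suffices. Record a missed 6-month visit as missing data, not as a withdrawal to be replaced.
- **Section 8.1.** Replace the meaningful-data qualifier with: all randomised subjects, in the arm assigned, each time-point comparison using every subject with a PEV sample at that time, on or off drug. Exclude only samples covered by section 5.7.4.
- **Reporting.** Add a table of missing samples at 48 hours and 6 months, with reasons, by arm.

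The cost is protocol and SAP wording and one table. The sampling is what section 3.9.1 already describes, though confirming that it governs is part of the reconciliation. The downside, if replacement is dropped, is possibly fewer than 60 completers. Under the section 8.2 inputs, and with Appendix E unseen, t-test power stays above 90% down to 23 per arm, and Mann–Whitney on normal data down to about 24 per arm.
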